9.3 Estimands

The primary efficacy analysis will evaluate the ‘hypothetical’ estimand in anti-AChR or anti-MuSK autoantibody-positive participants with generalized MG who experience moderate to severe symptoms and are being considered for additional treatment such as IVIg or PEX, where the main intercurrent events are the use of rescue medication prior to Day 43 and treatment discontinuation (or withdrawal from study) due to TEAEs. The primary efficacy analysis is the change from Baseline in MG-ADL score to Day 43 (Visit 10).

A hypothetical strategy will be used for rescue medication, ie, the intervention effect will be estimated under the hypothetical condition where rescue medication is not given. In the case of TEAEs leading to treatment discontinuation, observed data after treatment discontinuation will be utilized where possible.

The reason why a hypothetical estimand approach has been selected as the primary approach is because the use of rescue medication is likely to have a significant effect on subsequent efficacy data and for those study participants who discontinue treatment due to AEs, they are likely to also commence rescue medication in which case the hypothetical strategy will be applied once rescue medication has been initiated.

Missing data will be imputed under a missing at random assumption.

Data handling conventions for data affected by COVID-19 will be detailed fully in the SAP.

To check the assumptions of the primary analysis and definition of the Estimand, sensitivity and supplemental analyses of the change from Baseline in MG-ADL score to Day 43 (Visit 10) will be provided and are detailed in [Table 9-1](#).

Table 9-1: Estimand Details and Attributes

Objective Clinical Category	Statistical Category	Estimand			
		Variable/Endpoint	Population	IES	PLS (Analysis)
Primary Objective: To demonstrate the clinical efficacy of rozanolixizumab in patients with gMG					

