MG-ADL	Primary	Change from Baseline to Day 43 (Visit 10) in MG-ADL score	RS	The main intercurrent events are the use of rescue therapy prior to Day 43 (Visit 10) and treatment discontinuation (or withdrawal from study) due to TEAEs. A hypothetical strategy will be used for rescue therapy, i.e., the intervention effect will be estimated under the hypothetical condition where rescue therapy is not given. The same strategy will be used for TEAEs leading to treatment discontinuation.	Difference in mean change from Baseline (LSMD from CfB MMRM) to Day 43 (Visit 10) in the MG-ADL score for participants receiving rozanolixizumab versus placebo. Under MMRM, missing values are assumed to be Missing at Random (MAR).
MG-ADL	Sensitivity	Change from Baseline to Day 43 (Visit 10) in MG-ADL score	FAS	Hypothetical strategy , as for the primary analysis.	Difference in mean change from Baseline (LSMD from CfB MMRM) to Day 43 (Visit 10) in the MG-ADL score for participants receiving rozanolixizumab versus placebo. Under MMRM, missing values are assumed to be MAR.
MG-ADL	Sensitivity	Change from Baseline to Day 43 (Visit 10) in MG-ADL score	RS	Hypothetical strategy , as for the primary analysis.	Difference in mean change from Baseline (LSMD from CfB MMRM) to Day 43 (Visit 10) in the MG-ADL score for participants receiving rozanolixizumab versus placebo. A Jump-to-reference multiple imputation

Objective Clinical Category	Statistical Category	Estimand			
		Variable/Endpoint	Population	IES	PLS (Analysis)
					approach will be utilised to assess the validity of the MAR assumption. Missing data across all treatment groups will be imputed using the placebo distribution.

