8.1 Handling of intercurrent events

The main intercurrent events (ICEs) of interest are:

- ICE1 – The use of rescue therapy prior to Day 43 (Visit 10)
- ICE2 – Permanent treatment discontinuation (or withdrawal from study) due to TEAEs

Two additional types of ICEs will be included to account for data affected by the COVID-19 pandemic as follows:

- ICE3 – Treatment discontinuation due to suspected/confirmed COVID-19 infection (“Confirmed COVID-19” or “Suspected COVID-19” as the relationship to COVID-19 in the COVID-19 Impact eCRF)
- ICE4 – Treatment discontinuation due to non-COVID-19 infection related issues (“General circumstances around COVID-19 pandemic without infection” or “other” as the relationship to COVID-19 in the COVID-19 Impact eCRF)

The number and percentage of study participants with each intercurrent event will be summarized by treatment group and RLZ total.

The strategies to handle ICEs are summarized as below:

Strategies	Description
Hypothetical & treatment policy strategy	
If study participants experience ICE1, data at and after the point of the ICE for the purpose of analysis will be treated as missing and imputed under proposed method per Section 4.2.1.
 
For participants experiencing ICE2-4, data in the Treatment Period from Baseline to Day 43 will be used regardless of whether any ICEs occurred, missing data will be imputed per Section 4.2.1.
 
For participants who permanently discontinue treatment or withdraw from the study during Treatment Period and who continue into the Observation Period, the observation phase data (collected bi-weekly) will be mapped to the nearest visit for primary analysis where treatment windows will be utilized for the mapping.

Treatment policy strategy	The data in the Treatment Period from Baseline to Day 43 will be used regardless of whether any intercurrent events occurred.
Composite strategy	The occurrence of any intercurrent events above will be handled by evaluating the corresponding study participants as treatment failures and imputed with a worst score (continuous) or non-responder (binary).
COVID-19 Hypothetical strategy	
If participant experience ICE1 and/or ICE2, then data at and after the point of the intercurrent event for the purpose of analysis will be treated as missing.
 
Additionally, participant experience ICE3, ICE4 or those that have visits in treatment period affected (e.g. visit performed by video call) will be completely removed from analysis.

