8.2.2 Primary analysis of the primary efficacy endpoint

The primary analysis is based on the RS under the hypothetical & treatment policy strategy (see details in [Section 8.1](#)). Any missing MG-ADL scores (including missing data after the intercurrent events) will be handled based on maximum likelihood estimation method under MAR assumption.

A stage-wise MMRM with treatment group, Baseline MG-ADL score, region, stratification factor(s) including MuSK(+/-) and /or AChR(+/-), and treatment group by day (interaction term) as fixed factors and study participant as a random effect. The MMRM will include Days 8, 15, 22, 29, 36 and 43.

The model will utilize an unstructured covariance pattern for the repeated measures. If the model does not converge using the unstructured pattern, then an autoregressive covariance structure

will be used. The Kenward-Roger approximation will be used to estimate the denominator degrees of freedom.

For each stage, the least squares means (LSMs) of each treatment group, and the least squares mean differences (LSMDs) between each dose group and placebo will be reported for Day 43 (Visit 10), along with the corresponding 2-sided 97.5% CIs and p-values.

The study follows a 2-stage group sequential adaptive design using combination test (Lehmacher and Wassmer, 1999) based on the inverse-normal method of combining independent stagewise p-values (Hedges and Olkin, 1985)

The analysis takes into account that the study is a 2-stage group sequential adaptive design assuming equal weighting of each stage, with weights = $1/\sqrt{2}$:

- Stage 1 – Cohort up to the formal IA
- Stage 2 – Cohort post-IA

The following sequential test statistic will be used to test the global null hypothesis at the end of stage 2:

$$T = \sum_{i=1}^2 w_i \phi^{-1}(1 - p_i)$$

Where subscript $i = 1, 2$ represents the stage, p_i represents the appropriate multiplicity adjusted p-value at stage i (for example at stage 1, $p_1 = \min(2 * p_{\min}, 1)$ where p_{\min} is the minimum of the two nominal p-values), the weights $w_{ki} = 1/\sqrt{2}$ satisfy $\sum_{i=1}^2 w_{ki}^2 = 1$ and ϕ^{-1} is the inverse cumulative standard normal distribution function. The test statistic T and $z = \phi^{-1}(1 - p_i)$ have a standard normal distribution, (Lehmacher and Wassmer, 1999).

The combined p-value (2-sided) for the 2 stages, which tests the global null hypothesis, can be calculated by:

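### Protocol Table 9-1 contradicts Protocol 9.3 and the SAP on data after discontinuation for TEAEs, and the SAP's COVID-19 analysis changes the handling of those data as well as of COVID-19

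*Protocol*

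**What the plan says.** Protocol 9.3 applies a hypothetical strategy to rescue. For participants who stop because of TEAEs, the text says "observed data after treatment discontinuation will be utilized where possible", and the hypothetical strategy takes over only once rescue has begun. The primary row of Table 9-1, in the same section, first sets the hypothetical strategy for rescue and then says of the other event: "The same strategy will be used for TEAEs leading to treatment discontinuation".

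The SAP defines ICE2 as "Permanent treatment discontinuation (or withdrawal from study) due to TEAEs". Under the strategy it names Hypothetical & treatment policy, SAP 8.1 sets data to missing from ICE1 (rescue) onward, but "For participants experiencing ICE2-4, data in the Treatment Period from Baseline to Day 43 will be used regardless of whether any ICEs occurred". SAP 8.2.2 adopts this rule: "The primary analysis is based on the RS under the hypothetical & treatment policy strategy". SAP 3.9 lists, among changes from the protocol, a general update of the estimands and intercurrent-event strategies after regulatory feedback. It names no event.

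SAP 8.1 also defines a COVID-19 Hypothetical strategy. "If participant experience ICE1 and/or ICE2, then data at and after the point of the intercurrent event" are treated as missing. A second sentence, beginning "Additionally, participant experience ICE3, ICE4 or those that have visits in treatment period affected", removes those participants from the analysis entirely. SAP 8.2.5 applies this strategy to the primary endpoint, and SAP 8.3.2 to 8.3.6 repeat it for the five continuous secondary endpoints.

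**The concern.** The two rules for ICE2 answer different questions. One estimates the effect whether or not participants stopped for side effects; the other estimates the effect had nobody stopped for them. The protocol states both for the same primary estimand, and they cannot both hold for someone who stops for a TEAE and does not receive rescue.

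Stopping may also be unbalanced. Protocol 2.2 and 4.3 report more frequent and more severe headache on rozanolixizumab than on placebo, and Protocol 7.1.3 lists certain related headaches among the events requiring permanent discontinuation. If benefit fades after stopping, masking the later scores favours the active arms.

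The COVID-19 analysis raises a separate problem. Its use is to show whether the pandemic affected the result, and that requires COVID-19 handling to be the only thing that differs from the primary analysis.

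**Working it through.** **Side by side.** What each place does with the data:

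| Place | After rescue (ICE1) | After TEAE discontinuation (ICE2) | COVID-affected participants |
|---|---|---|---|
| Protocol 9.3 text | hypothetical | observed scores used | left to the SAP |
| Protocol Table 9-1, primary row | hypothetical | hypothetical | not stated |
| SAP 8.1 and 8.2.2, primary | missing | observed scores used | ICE3 and ICE4: observed scores used |
| SAP 8.1 COVID-19 strategy | missing | missing | removed |

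Rows 1 and 3 agree on ICE2, and row 2 is the outlier. Rows 3 and 4 differ in two columns, so a difference between those two analyses has two possible sources.

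**Spread of the Table 9-1 rule.** Three MG-ADL sensitivity rows (FAS, jump-to-reference, all six doses) take their strategy from the primary row. So do a secondary and a sensitivity row for each of five continuous secondary endpoints: 3 + 5 × 2 = 13 rows.

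**Whether later scores would exist.** Under Protocol 7.1.3, participants who must stop permanently move into the Observation Period. SAP 8.1 maps Observation Period scores to the nearest treatment visit for the primary analysis. The choice of rule can therefore change the data analysed.

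**The plan's own figures.** The documents quantify nothing on ICE2. The power values in SAP Table 2-1 were checked by simulating the two-stage design (100,000 runs per scenario): scenario 4 gave 0.763 against a stated 0.750, and scenario 7 gave 0.951 against 0.943. All seven scenarios checked were within 2 percentage points. These figures take an effect and an SD as inputs, with no ICE2 rule, so this point does not alter them.

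**Illustrative size.** Gap between the rules = E × p × f, where:
- E is the effect on drug, 1.5 to 2.0 points (SAP 2.4).
- p is the ICE2 rate in an active arm. Assumed 2% to 20%, with 0% on placebo.
- f is the share of benefit lost by Day 43 after stopping. Assumed 0.5 to 1.0.

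Masked participants are taken to be predicted at the full effect.

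- E = 1.5: from 1.5 × 0.02 × 0.5 = 0.015 to 1.5 × 0.20 × 1.0 = 0.30 points.
- E = 2.0: from 2.0 × 0.02 × 0.5 = 0.02 to 2.0 × 0.20 × 1.0 = 0.40 points.

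For scale, with 60 per arm (30 in Stage 1 plus the Stage 2 minimum of 30) and SD 3.5, SE = 3.5 × √(2/60) = 0.64. The range at E = 1.5 is then 0.015/0.64 = 0.02 to 0.30/0.64 = 0.47 standard errors.

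These gaps assume that every ICE2 participant has a usable Day 43 score and no rescue. If a share r starts rescue first or has no later score, the gap shrinks roughly by the factor (1 − r). With r = 0.5 (assumed), 0.30 becomes 0.15.

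**The case against.** The strongest reply is that the primary analysis is not in doubt. SAP 8.1, 8.2 and 8.2.2 state one rule, the Protocol 9.3 text agrees with it, and SAP 3.9 declares an update. The change log for SAP Amendment 2 also records that the former hypothetical strategy was merged into the present combined one. This stands. A reader might infer two live primary analyses, or a silent switch of estimand, and the documents support neither. What remains is a wrong table row, the rows that inherit its rule, and a declaration that does not name the change.

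Second, other planned analyses keep scores after ICE2. Supplementary Analysis #2 uses treatment policy throughout. Sensitivity Analysis #4 excludes confirmed COVID-19 cases and keeps ICE2 scores under either of its two descriptions: treatment policy in SAP 8.2.3.4, the combined strategy in SAP 8.2 and Table 8-2. On the latter, comparing it with Sensitivity Analysis #1 changes one thing only. The COVID-19-free descriptive summaries (SAP 8.4.4, 8.4.6) mention no masking after ICE2. This also stands, in part: Sensitivity Analysis #4 covers confirmed cases only and its label is inconsistent, and the summaries are descriptive.

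Third, the size is assumed. Protocol 9.3 expects many who stop for adverse events to start rescue, after which the two rules treat their data alike. Protocol 4.2 reports that total IgG returned to baseline by about Day 57 in the single-dose study, so complete loss of benefit by Day 43 is doubtful for someone who stops late. A reader might infer a known bias towards active; the documents give no rate from which to establish one.

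Finally, the COVID-19 analysis is labelled additional and lies outside the testing procedure in SAP 4.6. That its ICE2 rule is left over from the former strategy is a plausible inference, but no text says so.

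**Conclusion.** The point holds on the text. The Table 9-1 primary row contradicts Protocol 9.3, and 13 further rows inherit its rule. The SAP settles the operative primary rule, so the primary analysis is not ambiguous.

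The COVID-19 analysis, followed as written, changes the handling of ICE2 and of COVID-19 together and gives no reason for the first. A difference from the primary result, for MG-ADL or any of the five continuous secondary endpoints, could not be attributed to COVID-19 alone.

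The size is unknown. The illustration gives about 0.02 to 0.30 points at an effect of 1.5 and up to 0.40 at 2.0. It rests on an assumed ICE2 rate confined to the active arms, assumed loss of benefit and usable later scores, so the upper end is probably generous. Confirmatory testing, power and sample size are unaffected. The correction is worth making because it is cheap and makes a planned analysis interpretable.

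**What to change.** 1. In the COVID-19 Hypothetical strategy of SAP 8.1, limit the masking to ICE1 and keep scores after ICE2 as in the primary analysis. Only the handling of COVID-affected participants then differs. If masking after ICE2 is intended, state the reason.
2. Restate the Table 9-1 primary row as hypothetical for rescue and treatment policy for discontinuation due to TEAEs. Relabel the 13 rows that cite it as Hypothetical & treatment policy; correcting the primary row alone would leave them under the old name.
3. In SAP 3.9, name the ICE2 change: from hypothetical in Table 9-1 to observed scores used, in line with the Protocol 9.3 text.

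The cost is wording only. Items 1 and 3 are an SAP amendment; item 2 is a protocol amendment, although confined to one table. No new data, visits or participants are needed.

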9.4 Planned Efficacy/Outcome Analyses

9.4.1 Analysis of the primary efficacy endpoint

Analysis of the primary efficacy variable will be listed and descriptive statistics will be generated for the observed values and changes from Baseline. Summary outputs will be presented by treatment group and visit.

The formal testing strategy proposed is a flexible combination test based on the inverse normal method (Lehmacher and Wassmer, 1999) with equal weighting of Stage 1 (up to the formal interim analysis) and Stage 2 (post-interim analysis) data. Confirmatory testing of single hypotheses is based on a closed-testing procedure. For the closed testing procedure the Bonferroni approach is used as the intersection test for testing the global and intersection hypotheses. If a dose other than that defined by the "Select the best dose (and any dose with a mean response not worse than 1 point than the selected "best dose")" option (see Section 9.8 for details) is chosen for Stage 2 the adjusted p-value for the chosen dose(s) will be used in the combination test.

The primary efficacy analysis of the study will include the cohort of study participants from Stage 1 (n=) and those who received the selected doses in Stage 2. The primary endpoint, Change from Baseline in MG-ADL, will be analyzed by stage-wise mixed model for repeated measures (MMRM) ANCOVA including a term for Baseline MG-ADL score, region, treatment group, the treatment group by week interaction term, and a term for the stratification factor (categorized as AChR or MuSK). The model will define patient as a random effect and utilize an unstructured covariance pattern. If the model does not converge using the unstructured pattern then an autoregressive covariance structure will be used.

The t-test statistics for each dose group (at each stage) will be used to calculate unadjusted p-values and these will be used to form the p-value combination test(s) as described above. The multiplicity introduced by having potentially 2 doses at the end of the study will be addressed by using a Bonferroni approach. The critical value for this test will be the upper 1.25% percentile of the standard normal distribution (because no alpha will be spent in Stage 1, the futility criterion is not binding and in Stage 2 the alpha is divided between the 2 doses). Similar presentations within each stratification factor may be provided.

9.4.2 Analysis of secondary and other efficacy endpoints

All continuous secondary efficacy variables will be analyzed using the combination testing strategy and model defined for the primary analysis. The binary secondary efficacy variable of MG-ADL responder (≥ 2.0 points improvement from Baseline) at Day 43 (Visit 10) will be analyzed using logistic regression, including a term for Baseline MG-ADL score, treatment group, and a term for the stratification factor (categorized as AChR or MuSK).

In addition, all continuous secondary efficacy variables will be listed and summarized descriptively by treatment group and week. Descriptive statistics will be generated for the observed values and the change from Baseline. For the binary variable, frequency counts and percentages will be produced.

A sequential hierarchical test procedure will be applied to protect the overall significance level for the multiplicity of endpoints. The predefined order of formal hypotheses testing for the secondary endpoints will be performed in the following sequence:

- Change from Baseline to Day 43 (Visit 10) in MG-C score.
- Change from Baseline to Day 43 (Visit 10) in QMG score.
- Change from Baseline to Day 43 (Visit 10) in the MG Symptoms PRO ‘Muscle Weakness Fatigability’ score.
- Change from Baseline to Day 43 (Visit 10) in the MG Symptoms PRO ‘Physical Fatigue’ score.
- Change from Baseline to Day 43 (Visit 10) in the MG Symptoms PRO ‘Bulbar Symptoms’ score.

All other variables will be listed and summarized descriptively. Time to first MG-ADL response (defined as ≥ 2.0 point improvement from Baseline) will be analyzed using a Cox Proportional Hazards model including a fixed term for treatment, and a term for the stratification factor (categorized as AChR or MuSK). The statistical model will be applied to each stage and the results combined using in a similar fashion to the primary analysis. An overall study used to

calculate the Hazard Ratio (test/reference), 95% CI and p-values for each treatment comparison of interest will be presented. The time to first MG-ADL response will be presented graphically using a Kaplan-Meier curve. Study participants will be censored at time of initiation of rescue therapy or end of treatment.

Further exploratory analysis may be performed using adequate statistical methods; details will be provided in the SAP.

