6.5.4 Rescue therapy

Rescue therapy for the study will consist of IVIg or PEX. The study site will supply rescue therapy that will be obtained locally.

Study participants who experience disease worsening (eg, an increase of 2 points on the MG-ADL or 3 points on the QMG scale between two consecutive visits) may be considered for rescue therapy at the discretion of the Investigator.

Study participants who need rescue therapy during the Treatment Period may receive IVIg or PEX at the discretion of the Investigator, will complete any subsequent visit(s) and will move into the Observation Period.

For study participants receiving IVIg or PEX as rescue therapy, the date and time of administration as well as the name and dosage regimen of the rescue therapy must be recorded.

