MG-ADL	Secondary	MG-ADL responder (≥ 2.0 points improvement from Baseline) at Day 43 (Visit 10)	RS	The main intercurrent events are the use of rescue therapy prior to Day 43 (Visit 10) and treatment discontinuation (or withdrawal from study) due to TEAEs. The intercurrent events will be handled using a composite strategy , ie, the occurrence of an intercurrent event will be handled by evaluating the corresponding participants as nonresponders.	Odds ratio at Day 43 (Visit 10) analyzed using logistic regression model adjusting for covariates for participants receiving rozanolixizumab versus placebo.
MG-C	Secondary	Change from Baseline to Day 43 (Visit 10) in MG-C score	RS	Hypothetical strategy , as described for the primary analysis of MG-ADL endpoint.	Difference in mean change from Baseline (LSMD from CfB MMRM) to Day 43 (Visit 10) in the MG-C score for participants receiving rozanolixizumab versus placebo. Under MMRM, missing values are assumed to be MAR.
MG-C	Sensitivity	Change from Baseline to	RS	Hypothetical strategy , as	Difference in mean change from Baseline

Objective Clinical Category	Statistical Category	Estimand			
		Variable/Endpoint	Population	IES	PLS (Analysis)
		Day 43 (Visit 10) in MG-C score		described for the primary analysis of the MG-ADL endpoint.	(LSMD from C _{if} B MMRM) to Day 43 (Visit 10) in the MG-ADL score for participants receiving rozanolixizumab versus placebo. A Jump-to-reference multiple imputation approach will be utilised to assess the validity of the MAR assumption. Missing data across all treatment groups will be imputed using the placebo distribution.

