4.2 Handling of dropouts or missing data

4.2.1 Efficacy data

The rules for handling missing data of individual items in the calculation of the QMG, MG-C, MG-ADL, MG Symptom PRO, MGII, and MG-QOL15r scores at a certain visit are described in [Section 13.1](#), [Section 13.2](#), [Section 13.3](#), [Section 13.4](#), [Section 13.5](#) and [Section 13.6](#), respectively.

Imputation methods for missing overall scores (including missing data due to intercurrent events [Section 8.1](#)) for the analyses of primary and secondary endpoints are listed as below. The estimand corresponding to these analyses are described in [Section 8](#).

Efficacy Endpoints	Statistical Analysis Type	Statistical Analysis Methods	Imputation Methods
Primary	Primary	MMRM	Imputation: maximum likelihood estimation
	Sensitivity 1	MMRM	Imputation: maximum likelihood estimation
	Sensitivity 2	MMRM	Imputation: J2R
	Sensitivity 3	MMRM	Imputation: maximum likelihood estimation
	Sensitivity 4	MMRM	Imputation: maximum likelihood estimation
	Supplemental 1	Trimmed Mean using ANCOVA	Imputation: worst score
	Supplemental 2	MMRM	Imputation: maximum likelihood estimation
Secondary (continuous)	Secondary	MMRM	Imputation: maximum likelihood estimation
	Sensitivity	MMRM	Imputation: J2R
	Supplemental	Trimmed Mean using ANCOVA	Imputation: worst score
Secondary (binary)	Secondary	Logistic model	Imputation: NRI

MMRM=mixed model for repeated measures; ANCOVA= analysis of covariance; J2R=Jump to reference; NRI= nonresponse imputation

For other binary efficacy endpoints (e.g. QMG responder), missing data will be imputed using nonresponse imputation (NRI). That is, study participants with missing data at the timepoint of interest, and all timepoints after use of rescue medication will be treated as non-responders.

For ordinal endpoints (EQ-5D-5L, PGI-S, PGI-C), the observed case method will be applied. No further imputation is used.

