8.4.3 Time to MG-ADL response (≥ 2.0 points improvement from Baseline)

Time to MG-ADL response (in days) is defined as Date of First MG-ADL Response— Date of MG-ADL Baseline + 1.

Study participants who use rescue therapy prior to Day 43 or who are withdrawn from the treatment/study due to TEAEs before achieving first MG-ADL response will be censored at time of event. Study participants who never achieve a response by Day 43 will be censored at the date of their last MG-ADL assessment.

The number of study participants with 8, 12, 24, 32, 43 days to first MG-ADL response and number of censored study participants will be summarized descriptively.

Time to first MG-ADL response will be analyzed using a Cox Proportional Hazards model including fixed terms for treatment and stratification factors (MuSK+/- or AChR+/-). This model will be performed separately for study participants included in the interim analysis and for all study participants overall. Region may be added as an additional factor in the Cox Proportional Hazards model if it is significant in the primary analysis.

The Hazard Ratio (test/reference), 95% CI and p-values for each treatment comparison of interest will be presented for the Stage 1 (interim analysis), Stage 2 and overall (all data combined).

The log-hazard ratio, standard error estimates and (1-sided) p-values from the separate stage-wise Cox Proportional Hazards models for the relevant treatment group will be used to create overall p-values and repeated confidence intervals using the same methodology as the primary efficacy analysis.

The time to first MG-ADL response will be presented graphically using a Kaplan-Meier curve by treatment group, RLZ total. See details in [Section 9.3.2](#).

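### Censoring at rescue and at TEAE withdrawal makes the Kaplan-Meier curve for time to MG-ADL response overstate the share who respond first, and the TEAE rule does not fit the SAP's own handling of that event

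*Protocol*

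**What the plan says.** Time to first MG-ADL response (a 2-point improvement) is one of the other efficacy endpoints, below the secondary tier.

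- **Censoring, Protocol 9.4.2:** "Study participants will be censored at time of initiation of rescue therapy or end of treatment".
- **Censoring, SAP 8.4.3:** the rescue rule is kept, and participants "who are withdrawn from the treatment/study due to TEAEs before achieving first MG-ADL response will be censored at time of event". For the rest, "Study participants who never achieve a response by Day 43 will be censored at the date of their last MG-ADL assessment".
- **Display and model, SAP 8.4.3:** "The time to first MG-ADL response will be presented graphically using a Kaplan-Meier curve by treatment group, RLZ total", and "Time to first MG-ADL response will be analyzed using a Cox Proportional Hazards model including fixed terms for treatment and stratification factors". Stage-wise results are combined into overall p-values and repeated confidence intervals.

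Neither document states an estimand for this endpoint, a competing-risk display, or a sensitivity analysis of the censoring.

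The same two events are treated differently elsewhere:

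- **Day 43 MG-ADL responder (Protocol Table 9-1; SAP 8.1 and 8.3.1):** composite strategy. The intercurrent event "will be handled by evaluating the corresponding participants as nonresponders".
- **Other binary efficacy endpoints (SAP 4.2.1):** "all timepoints after use of rescue medication will be treated as non-responders".
- **Primary analysis (SAP 8.1):** scores at and after rescue are set to missing. Treatment Period scores after TEAE discontinuation are used, and Observation Period scores are mapped to the nearest visit.

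**The concern.** Kaplan-Meier assumes that a participant censored today has the same later chance of response as those still under observation. Rescue is a doubtful case for that assumption. The example of worsening in Protocol 6.5.4 is "an increase of 2 points on the MG-ADL or 3 points on the QMG scale between two consecutive visits", which is a move away from response. The decision is left to the investigator and the thresholds are only an example, so the link is plausible rather than mechanical.

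There is a second issue, which does not depend on prognosis. Most readers will take the curve as the proportion of an arm that has responded by a given day. With rescue and withdrawal censored it is not that proportion. It is the proportion that would have responded if nobody had been rescued or withdrawn and those participants had then behaved like the others.

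This matters because Protocol 4.3 gives time to onset of symptom relief as one reason for including the higher dose, and this analysis addresses that question directly.

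**Working it through.** The plan states no response rate, rescue rate, hazard ratio or power for this endpoint, so there is no figure to reproduce. The calculation below compares the planned curve with the share who respond before rescue or withdrawal.

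**Inputs.** Six weekly assessments, Days 8 to 43 (SAP 8.2.2). Assumed, because the documents do not give them: response by Day 43 of 25% to 75%, and 0% to 20% of an arm rescued or withdrawn for a TEAE before first response.

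**Formulas.** Let h be the weekly probability of first response among those at risk. Let c be the probability of rescue or withdrawal among non-responders after each of visits 1 to 5. Put q = (1 − h)(1 − c).

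- Planned curve at Day 43: 1 − (1 − h)^6
- Cumulative incidence of response before either event: h(1 − q^6)/(1 − q)
- Event share: (1 − h)c(1 − q^5)/(1 − q)

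h and c are solved to match the assumed response and event shares.

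**One case in full: 60% respond, 10% have the event first.** The solution is h = 0.1576 and c = 0.0344, so q = 0.8424 × 0.9656 = 0.8134.

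- Cumulative incidence: 0.1576 × (1 − 0.8134^6)/(1 − 0.8134) = 60.0%
- Event share: 0.8424 × 0.0344 × (1 − 0.8134^5)/(1 − 0.8134) = 10.0%
- Planned curve: 1 − 0.8424^6 = 64.3%
- Excess: 4.3 points

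**Excess of the planned curve at Day 43, in points:**

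| Cumulative incidence of response | 3% events | 5% | 10% | 20% |
|---|---|---|---|---|
| 30% | 0.5 | 0.9 | 1.8 | 3.9 |
| 45% | 0.8 | 1.4 | 2.9 | 6.5 |
| 60% | 1.2 | 2.0 | 4.3 | 9.8 |
| 75% | 1.6 | 2.8 | 6.1 | 15.0 |

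With no events the excess is zero. At 5% to 10% events it runs from 0.9 to 6.1 points. It rises across each row and down each column.

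**What this does to the gap between arms (response / events before response):**

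| Case | Placebo | Active | Excess, placebo | Excess, active | Gap shown | Gap in cumulative incidence |
|---|---|---|---|---|---|---|
| a | 40% / 10% | 70% / 3% | 2.5 | 1.5 | 29.0 | 30.0 |
| b | 25% / 5% | 70% / 4% | 0.7 | 2.0 | 46.3 | 45.0 |
| c | 40% / 7% (5% rescue, 2% TEAE) | 65% / 10% (1% rescue, 9% TEAE) | 1.7 | 4.8 | 28.1 | 25.0 |
| d | 40% / 5% | 70% / 5% | 1.2 | 2.5 | 31.3 | 30.0 |

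In case a the gap narrows. In b, c and d it widens. In b the arm with fewer events is inflated more.

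**Limit of the calculation.** It treats both events as ending the chance of response. Participants who stop for a TEAE may still respond later, and their recorded scores would show it. The TEAE part of case c is therefore the excess over response before withdrawal, not over response by Day 43 whatever happens to treatment.

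**Hazard ratio.** In case c the cause-specific ratio, ln(1 − h) active over placebo, is 2.22. The same ratio on ln(1 − cumulative incidence) is 2.06. In case a the pair is 2.27 and 2.36. A simulation of weekly scores, with assumed true Day 43 mean changes of −3 active and −1 placebo and rescue as the only event, gave 1.61 against 1.62 (13% placebo and 7% active rescued) and 1.58 against 1.61 (25% and 13%).

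**The case against.** **Censoring at rescue is an estimand choice, not an error.** The primary estimand asks what would happen without rescue, and censoring at rescue is its time-to-event counterpart. This stands. On that reading the curve is too high only if rescued participants had a below-average chance of response, which is plausible but not quantified in the documents.

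**The Cox result survives.** It is a valid cause-specific hazard ratio. Keeping rescued participants at risk would estimate a different quantity, not correct this one. This also stands.

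**The protocol may already censor at TEAE withdrawal.** Its end-of-treatment wording could cover premature end of treatment, since Visit 10 carries both labels in the schedule. The primary row of Table 9-1 also applies the hypothetical strategy to TEAE discontinuation. But the text of Protocol 9.3 says observed data after such discontinuation are used where possible, and SAP 8.1 adopts that for the primary analysis. SAP 8.4.3 is out of line with it, whatever its origin.

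**Much of the composite picture is available elsewhere.** SAP 8.4.9 tabulates observed and imputed responders by visit, SAP 8.4.3 tabulates first responses and censored participants by day, and SAP 8.4.2 analyses time to first rescue. This limits the harm but does not change what the curve displays.

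**Stronger readings to avoid.** A reader might infer that the arm with more rescue is always inflated most, so that the plan understates the drug effect. Cases b to d show otherwise. A reader might also expect the curve to agree with the Day 43 responder rate once corrected. It need not: first response at any visit and response at Day 43 differ even with no rescue, because a response can be lost.

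**Conclusion.** The point holds in a limited form. As a picture of the share of randomised participants who respond before rescue or withdrawal, the planned Kaplan-Meier curve is never too low, and it is too high whenever such events precede later responses. The size is about 1 to 6 points at Day 43 for 5% to 10% events, and 0 to 15 points over the whole assumed range. These figures rest on assumed rates and on constant weekly probabilities. The direction of the effect on the gap between arms cannot be stated in advance.

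Censoring at rescue is defensible under the primary strategy, though plausibly informative. Censoring at TEAE withdrawal is the weaker rule: the SAP primary analysis uses those scores, and the responder endpoint calls those participants non-responders. Neither rule leads to censoring.

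Severity is low. The endpoint is outside the multiplicity procedure in SAP 4.6, and no confirmatory conclusion depends on it. The documents do not support calling the Cox analysis invalid or the treatment comparison biased in a known direction.

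**What to change.** In SAP 8.4.3:

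1. State the estimand for this endpoint.
2. Present the cumulative incidence of first response with rescue as a competing event, in place of the Kaplan-Meier curve or beside it. With complete follow-up this equals keeping rescued participants as non-responders to Visit 10.
3. Do not censor at TEAE discontinuation. Use the MG-ADL scores collected up to Day 43, with Observation Period visits mapped as in SAP 8.1. Participants with no later scores fall under the existing rule of censoring at the last assessment.
4. Keep the Cox model censored at rescue, and label the result a cause-specific hazard ratio.

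Align Protocol 9.4.2 if it is amended for other reasons. No new data are needed. The cost is one more derivation and one more display, and the displayed response percentages will be slightly lower.
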